3.4 TERTIARY/EXPLORATORY ENDPOINT(S) ANALYSIS IN PART A

3.4.1 Definition of endpoint(s)

The tertiary endpoints detailed in this section are mentioned in Table 1 under [Section 1.2](#) for Part A. Refer to [Section 3.3.1](#) for the details of MSIS-29v2 and MSWS-12 assessments.

3.4.2 Main analytical approach

All tertiary efficacy endpoints in Part A will be analyzed using the randomized and treated population. All measurements collected after the treatment status change during the planned treatment period for participants who discontinue the IMP or permanently modify the background DMT will be included in the analysis.

Tertiary endpoints are all continuous endpoints. Summary statistics including mean, standard deviation, median, interquartile range (Q1, Q3), minimum, and maximum will be provided at scheduled visits in Part A. Only participants with baseline and at least one post-baseline assessment will be summarized. A similar MMRM approach as described for the primary endpoint of Part A in [Section 3.2.2.1](#) will be used, except that the log-transformed baseline sNfL levels will be replaced by the baseline values of the corresponding endpoint. Appropriate transformation will be used if necessary (eg, log-transform). Plots of least squares means (\pm standard error) over time will be provided. Plots of mean (\pm SE) and/or mean change (\pm SE) over time will also be provided.

No sensitivity or subgroup analyses will be conducted.

3.5 MULTIPLICITY ISSUES

Not applicable.

3.6 SAFETY ANALYSES

All safety analyses will be performed on the safety population as defined in [Section 2](#), unless otherwise specified, using the following common rules:

- The analysis of the safety variables will be essentially descriptive, and no testing is planned.
- Safety data in participants who do not belong to the safety population (eg, exposed but not randomized) will be provided separately.

In Part A, the safety analyses will be carried out with participants by the actual treatment received, irrespective of the treatment the participant has been randomized to.

Part A + Part B Safety Analyses

For categorical safety measures, such as AE, PCSA, shift summaries, data throughout both Part A and Part B will be summarized in three groups:

- Placebo/SAR443820 group includes participants who actually received placebo in Part A and SAR443820 in Part B. For participants in this group, only the data during SAR443820 exposure in Part B will be summarized. The baseline will be defined as the last available value prior to the first dose of SAR443820 in Part B.
- SAR443820/SAR443820 group includes participants who actually received SAR443820 in Part A, regardless of whether they entered Part B. For participants in this group, all data during SAR443820 exposure will be summarized. The baseline will be defined as the last available value prior to the first dose of the study intervention (same baseline defined for Part A in [Section 3.1](#)).
- Overall SAR443820 group includes participants from Placebo/SAR443820 group and SAR443820/SAR443820 group.

For continuous safety measures collected at longitudinal time point, such as labs and vital signs, data throughout both Part A and Part B will be summarized in two groups:

- Placebo/SAR443820 group includes participants who actually received placebo in Part A, regardless of whether they enter Part B. For participants in this group, all data during the on-treatment period of Part A and Part B will be summarized at each protocol scheduled visit. The baseline will be defined as the last available value prior to the first dose of study intervention (same baseline defined for Part A in [Section 3.1](#)).
- SAR443820/SAR443820 group includes participants who actually received SAR443820 in Part A, regardless of whether they entered Part B. For participants in this group, all data during the on-treatment period of Part A and Part B will be summarized at each protocol scheduled visit. The baseline will be defined as the last available value prior to the first dose of study intervention (same baseline defined for Part A in [Section 3.1](#)).

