- 48-week double-blind treatment period (Part A)
- 48-week open-label long-term extension period (Part B)

Number of participants:

Approximately 280 participants will be screened to achieve 168 participants randomly assigned at a 1:1 ratio to SAR443820 or placebo (based on a 40% screen failure rate). A minimum of 50% of study participants are required to have progressive multiple sclerosis (PMS) (PPMS and SPMS).

Intervention groups and duration:

Study intervention(s)

SAR443820 OR matching placebo

Investigational medicinal product(s)

- Formulation: Both SAR443820 20 mg and matching placebo will be formulated in tablets
- Route(s) of administration: Tablets will be taken orally. The suggested method for IMP administration is detailed in [Section 6](#).
- Dose regimen:
 - Part A:
 - Treatment arm: SAR443820, 20 mg QD
 - Placebo arm: Placebo QD
 - Part B:
 - Treatment arm: SAR443820, 20 mg QD

Noninvestigational medicinal products(s) (NIMP)

- Formulation: MRI contrast enhancing preparations
- Route(s) of administration: intravenous (IV)
- Dose regimen: as per respective country-specific labelling

Devices

Not applicable.

Poststudy access to study medication

Part B is an open-label long-term extension period up to Week 96 in which all eligible participants from Part A may rollover to Part B and receive open-label IMP. In addition to this open-label extension, poststudy access to study medication could be provided based on local/country regulations.

Duration of study intervention

Treatment duration is up to 48 weeks each in Part A and Part B.

Statistical considerations:

[figure not shown]
- **Primary endpoint:** Week 48 sNfL levels relative to baseline
- **Main secondary endpoints:**
 - Cumulative number of new Gd-enhancing T1 hyperintense lesions as detected by MRI at Week 48, defined as the sum of the individual number of new Gd-enhancing T1 hyperintense lesions at all scheduled visits starting after baseline up to and including the Week 48 visit
 - Cumulative number of new and/or enlarging T2 hyperintense lesions as detected by MRI, at Week 48, defined as the sum of the individual number of new and/or enlarging T2 lesions at all scheduled visits starting after baseline up to and including the Week 48 visit
 - Time to onset of 12 weeks confirmed disability progression (CDP) from baseline as assessed by the Expanded Disability Status Scale (EDSS) score

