3.6.2 Adverse events

General common rules for adverse events

All adverse events (AEs) will be coded to a lower-level term (LLT), preferred term (PT), high-level term (HLT), high-level group term (HLGT), and associated primary system organ class (SOC) using the Medical Dictionary for Regulatory Activities (MedDRA) version currently in effect at Sanofi at the time of database lock.

The AEs will be analyzed in the following 4 categories:

- Pre-treatment AEs: AEs that developed, worsened or became serious during the pre-treatment period.
- Treatment-emergent adverse events (TEAE)s for Part A: AEs that developed, worsened or became serious during the on-treatment period for Part A.
- Treatment-emergent adverse events (TEAE)s for Part B: AEs that developed, worsened or became serious during the on-treatment period for Part B.
- Post-treatment AEs: AEs that developed, worsened or became serious during the post-treatment period.

Similarly, if occurring, deaths will be analyzed in the pre-treatment, treatment-emergent, and post-treatment periods.

The primary AE analyses will be on TEAEs. Pre-treatment and post-treatment AEs will be described separately.

An AE with incomplete or missing date/time of onset (occurrence, worsening, or becoming serious) will be classified as a TEAE unless there is definitive information to determine it is a pre-treatment or a post-treatment AE.

If the assessment of the relationship to IMP is missing for an AE, this AE will be assumed as related to IMP. Missing severity will be left as missing.

Multiple occurrences of the same event in the same participant will be counted only once in the tables within a treatment period, using the maximum (worst) severity by treatment phase.

The AE tables will be sorted as indicated in [Table 4](#).

Table 4 - Sorting of AE tables

AE presentation	Sorting rules
SOC and PT	By the internationally agreed SOC order and decreasing frequency of PTs ^a
AESI category and PT	By AESI category (protocol order) and decreasing frequency of PTs ^a
PT	By decreasing frequency of PTs ^a

^a Sorting will be based on the SAR443820 treatment group incidence, alphabetic order in case of equal frequency.

Analysis of all adverse events in Part A and Part A + Part B

The overview of TEAE will be generated presenting the number (%) of participants with:

- Any TEAE
- Any severe TEAE
- Any treatment-emergent SAE
- TEAE leading to death
- Any TEAE leading to permanent intervention discontinuation of IMP

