- Any treatment emergent AESI
- Any TEAE considered by the investigator as related to IMP

An additional overview summary including the number and rate of events will be provided.

The AE summaries of [Table 5](#) will be generated with number (%) of participants experiencing at least one event.

Listings of SAEs from randomized participants, AEs from participants who are treated but not randomized, AEs leading to treatment/study discontinuation and severe AEs will be provided.

Table 5 - Analyses of adverse events

Type of AE	MedDRA levels
All TEAEs	Primary SOC and PT
Common TEAE ($\geq 2\%$ in any group)	PT
TEAEs related to IMP as per Investigator's judgment	Primary SOC and PT
TEAE by maximal intensity	PT
Treatment emergent SAEs	Primary SOC and PT
Treatment emergent SAEs related to IMP as per Investigator's judgment	Primary SOC and PT
Treatment emergent AESIs	AESI category and PT
TEAEs leading to permanent intervention discontinuation	Primary SOC and PT
TEAEs leading to death ^b	Primary SOC and PT
Pretreatment AEs	Overview ^a
Post-treatment AEs	Primary SOC and PT

Type of AE	MedDRA levels

a Will include the following AE categories: any AEs, any serious AEs, any AEs leading to death
 
b Death as an outcome of the AE as reported by the Investigator in the AE page
	

Analysis of deaths in Part A and Part A + Part B

In addition to the analyses of deaths included in [Table 5](#), the number (%) of participants in the following categories will be provided:

- Deaths during the treatment-emergent period and post-treatment period
- Deaths in non-randomized participants or randomized but not treated participants

Analysis of adverse events of special interest (AESIs) in Part A and Part A + Part B

Adverse events of special interest (AESIs) will be selected for analyses as indicated in [Table 6](#). Number (%) of participants experiencing at least one event will be provided for each event of interest. Tables will be sorted as indicated in [Table 4](#). A listing of AESIs will also be provided.

Table 6 - Selections for AESIs

AESIs	Selection
Pregnancy of a female participant or female partner of a male participant	Dedicated CRF page (AECAT="PREGNANCY DATA")
Symptomatic overdose (serious or non-serious) with IMP	Dedicated CRF page (AECAT="OVERDOSE DATA"; must be symptomatic and AESI marked "Y")
Convulsions, seizures	CMQsn00079 for selection and AESI marked "Y"

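### Part A + Part B adverse event tables set crude percentages over up to 48 weeks on drug beside percentages over up to 96 weeks, with no exposure-adjusted rate by event

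*SAP*

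**What the plan says.** Protocol 1.1 sets the time base: "Treatment duration is up to 48 weeks each in Part A and Part B". SAP 3.6 then defines three columns for categorical safety measures across both parts.

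- **Placebo/SAR443820**: participants given placebo in Part A and drug in Part B. For them, "only the data during SAR443820 exposure in Part B will be summarized".
- **SAR443820/SAR443820**: "SAR443820/SAR443820 group includes participants who actually received SAR443820 in Part A, regardless of whether they entered Part B". For them, "all data during SAR443820 exposure will be summarized".
- **Overall**: "Overall SAR443820 group includes participants from Placebo/SAR443820 group and SAR443820/SAR443820 group".

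SAP 3.6.2, under the heading "Analysis of all adverse events in Part A and Part A + Part B", says that the Table 5 summaries "will be generated with number (%) of participants experiencing at least one event". Table 5 covers TEAEs by system organ class and preferred term, SAEs, and AESIs by category and preferred term. The text on AESIs also specifies number and percentage.

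Three other outputs take time into account:

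- SAP 3.6.2: "An additional overview summary including the number and rate of events will be provided". No denominator or unit is given.
- SAP 3.6.1 reports total time on treatment in participant-years.
- SAP 3.6.3.1 plans Kaplan-Meier curves by group for first ALT or AST elevation, and for either with raised bilirubin.

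**The concern.** A crude percentage has meaning only with its observation time. Here two groups with different maximum times on drug stand side by side under the same statistic, and the Overall column mixes them in proportions that depend on how many placebo participants enter Part B. A reader who sees a higher percentage in the SAR443820/SAR443820 column cannot tell longer observation from higher risk.

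Long-term safety is a stated Part B objective, and the AESIs include convulsions and serious infections. For those categories, and for individual preferred terms, the SAP specifies no rate and no time-to-event display.

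**Working it through.** The plan states no adverse event rate and no rate ratio, so there is no planned figure to reproduce. The check asks how far the two percentages would differ if the risk on drug were the same in both groups.

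**Inputs from the documents.** 48 weeks per part, so 48 against 48 + 48 = 96 weeks (Protocol 1.1, SAP 3.6). Anticipated dropout of 17% (Protocol 9.4, SAP 4). A 14-day tail after the last dose (SAP 3.1).

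**Assumptions.** Equal constant hazard; 48-week risk p from 1% to 80%; the 17% applied to each part as exponential discontinuation; a share q of 80% or 100% of Part A completers rolling over. None of these comes from the safety sections.

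**Step 1, full exposure.** The 96-week risk is 1 − (1 − p)², so the ratio of percentages is 2 − p.

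**Step 2, with discontinuation.** Let R be the chance of an event while on drug in one 48-week part. A participant reaches the second part event-free and still treated with probability q(1 − p)(0.83). The longer-exposed group therefore has risk R + q(1 − p)(0.83)R, and the ratio is 1 + 0.83q(1 − p). At p = 5%, q = 1: 1 + 0.83 × 0.95 = 1.79. At p = 10%, q = 0.8: 1 + 0.83 × 0.8 × 0.90 = 1.60.

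| 48-week risk p | 96-week risk, full exposure | Ratio, full exposure | Ratio, 17% stop per part, all roll over | Ratio, 17% stop per part, 80% roll over |
|---|---|---|---|---|
| 1% | 1.99% | 1.99 | 1.82 | 1.66 |
| 5% | 9.75% | 1.95 | 1.79 | 1.63 |
| 10% | 19% | 1.90 | 1.75 | 1.60 |
| 30% | 51% | 1.70 | 1.58 | 1.46 |
| 80% | 96% | 1.20 | 1.17 | 1.13 |

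With 17% stopping per part and full rollover, mean exposure is 43.8 weeks against 43.8 + 0.83 × 43.8 = 80.1 weeks, a ratio of 1.83.

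**Step 3, the 14-day tail.** Comparing 98 with 50 weeks at full exposure, the ratio is [1 − (1 − p)^(98/48)] / [1 − (1 − p)^(50/48)], which is 1.91 at p = 5% and 1.86 at p = 10%. The tail changes little.

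**Step 4, early onset.** If a share f of the 96-week cumulative hazard falls in the first 48 weeks on drug, with no dropout, the ratio is [1 − (1 − p)^(1/f)] / p. For f = 0.9 it is 1.11 at p = 5% and 1.09 at p = 30%. For f = 1 it is 1.0.

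**Step 5, the remedy.** The first-event rate per 100 participant-years at risk under constant hazard is 100 × 52.18 × [−ln(1 − p)] / 48 whatever the length of follow-up. It is 5.58 in both groups at p = 5% and 11.45 in both at p = 10%, where the crude percentages are 5% against 9.75% and 10% against 19%.

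**Step 6, where the remedy misleads.** Take p = 10%, no dropout and all hazard in the first 48 weeks. Mean time at risk in those weeks is 0.10 × 48 / 0.10536 = 45.6 weeks. The longer-exposed group adds 0.90 × 48 = 43.2 event-free weeks. Its rate is 45.6 / (45.6 + 43.2) = 0.51 of the other group's, although the percentages are equal.

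**The case against.** The strongest reply is that much of this is already covered. The additional overview follows directly after a list of broad classes (any TEAE, severe, serious, fatal, leading to discontinuation, AESI, related), so its natural reading is a rate for each class. Exposure is tabulated by group, so the unequal time base is visible. Liver elevations have Kaplan-Meier curves. SAEs and AESIs are also listed individually. Safety is descriptive with no testing, and the placebo-controlled comparison is Part A, where planned duration is equal.

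Most of that stands, and it limits the point. It does not remove it: none of these outputs gives a rate by preferred term or by AESI category, and the overview's rate has no stated denominator. The absence of tests does not make side-by-side percentages comparable.

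A reader might infer three stronger things that the documents do not support.

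- *That equal risk would look nearly doubled throughout the tables.* This needs uncommon events, constant hazard and near-complete 96-week exposure. SAP 3.6 keeps participants who never enter Part B in the longer-exposed group, so full exposure would require everyone to roll over and stay on drug.
- *That ALT increases cannot be compared between the groups.* The Kaplan-Meier curves by group provide a time-based comparison.
- *That exposure is the only difference between the columns.* Placebo/SAR443820 contains only people who entered Part B, and its first 48 weeks on drug are open-label. The other group's are blinded. Rates correct neither.

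**Conclusion.** The point holds as a limited weakness of presentation. The Part A + Part B percentages by preferred term and AESI category rest on unequal time on drug, and the plan gives no rate at that level. Under an equal, roughly constant hazard, the distortion is up to nearly twofold for uncommon events. With 17% stopping per part and 80 to 100% rolling over, it is about 1.6 to 1.8 at 48-week risks of 5 to 10%. It falls to 1.13 to 1.20 at a risk of 80%, and to about 1.0 to 1.1 where 90% or more of the hazard falls in the first 48 weeks. The hazard shape, the event risks, the rollover share and the use of 17% per part are all assumptions. The gap is clearest for convulsions, serious infections and the preferred-term tables. Randomized Part A safety results are not affected.

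**What to change.** Keep the numbers and percentages, and make two changes in SAP 3.6.2.

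1. State the denominator and unit of the rate in the additional overview, for example events per 100 participant-years.
2. In the Part A + Part B versions of the Table 5 summaries of TEAEs, SAEs and AESI categories, add participants with a first event per 100 participant-years at risk. Table 6 needs no change, because it holds only the case-selection rules for AESIs.

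Time at risk should run from the first SAR443820 dose to the first event or the end of the treatment-emergent period, including the 14-day tail. The participant-years in SAP 3.6.1 cannot serve, because they run from first to last dose and do not stop at the first event.

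The cost is a small extra derivation for each event, from dates already needed to classify events as treatment-emergent. No new data are required. The downside is that a rate assumes a roughly constant hazard and can understate early-onset risk in the longer-exposed group. The percentages and Kaplan-Meier curves should therefore stay beside it. A footnote should say that rates do not remove the selection of Placebo/SAR443820 participants into Part B.

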3.6.1 Extent of exposure

The extent of IMP exposure will be assessed by the duration of IMP exposure and summarized within the safety population.

Duration of IMP exposure

Duration of IMP exposure in Part A is defined as last IMP administration date in Part A – first IMP administration date + 1 day, regardless of unplanned intermittent discontinuations. If the date of the last dose of IMP in Part A is missing, the duration of IMP exposure in Part A will be left as missing.

Duration of cumulative SAR443820 exposure in Part A + Part B is defined as the last dose date of SAR443820 – first dose date of SAR443820 +1 day, regardless of unplanned intermittent discontinuations. If the last dose date of SAR443820 is missing, this duration will be left as missing.

Duration of IMP exposure in Part A will be summarized quantitatively and categorically by the treatment group participants actually received in Part A (Placebo versus SAR443820):

- > 0 and \leq 12 weeks
- > 12 and \leq 24 weeks
- > 24 and \leq 36 weeks
- > 36 and \leq 48 weeks
- > 48 weeks

Duration of cumulative SAR443820 in Part A + Part B will also be summarized quantitatively and categorically by actual treatment (Placebo/SAR443820, SAR443820/SAR443820 and overall) within the safety population:

- > 0 and \leq 12 weeks
- > 12 and \leq 24 weeks
- > 24 and \leq 36 weeks
- > 36 and \leq 48 weeks
- > 48 and \leq 72 weeks
- > 72 and \leq 96 weeks
- > 96 weeks

Additionally, the cumulative duration of treatment exposure (expressed in participant-years) will be provided for Part A and Part A + Part B separately.

Treatment compliance

A given administration will be considered noncompliant if the participant did not take the number of administrations as required by the protocol. No imputation will be made for participants with missing or incomplete data.

Percentage of treatment compliance for a participant will be defined as the number of administrations that the participant was compliant divided by the total number of administrations that the participant was planned to take from the first administration of IMP up to the actual last administration of IMP.

Treatment compliance will be summarized quantitatively and categorically (<80%, \geq 80%) for Part A and Part A + Part B using the similar format as stated above for exposure.

3.6.2 Adverse events

General common rules for adverse events

All adverse events (AEs) will be coded to a lower-level term (LLT), preferred term (PT), high-level term (HLT), high-level group term (HLGT), and associated primary system organ class (SOC) using the Medical Dictionary for Regulatory Activities (MedDRA) version currently in effect at Sanofi at the time of database lock.

The AEs will be analyzed in the following 4 categories:

- Pre-treatment AEs: AEs that developed, worsened or became serious during the pre-treatment period.
- Treatment-emergent adverse events (TEAE)s for Part A: AEs that developed, worsened or became serious during the on-treatment period for Part A.
- Treatment-emergent adverse events (TEAE)s for Part B: AEs that developed, worsened or became serious during the on-treatment period for Part B.
- Post-treatment AEs: AEs that developed, worsened or became serious during the post-treatment period.

Similarly, if occurring, deaths will be analyzed in the pre-treatment, treatment-emergent, and post-treatment periods.

The primary AE analyses will be on TEAEs. Pre-treatment and post-treatment AEs will be described separately.

An AE with incomplete or missing date/time of onset (occurrence, worsening, or becoming serious) will be classified as a TEAE unless there is definitive information to determine it is a pre-treatment or a post-treatment AE.

If the assessment of the relationship to IMP is missing for an AE, this AE will be assumed as related to IMP. Missing severity will be left as missing.

Multiple occurrences of the same event in the same participant will be counted only once in the tables within a treatment period, using the maximum (worst) severity by treatment phase.

The AE tables will be sorted as indicated in [Table 4](#).

Table 4 - Sorting of AE tables

AE presentation	Sorting rules
SOC and PT	By the internationally agreed SOC order and decreasing frequency of PTs ^a
AESI category and PT	By AESI category (protocol order) and decreasing frequency of PTs ^a
PT	By decreasing frequency of PTs ^a

^a Sorting will be based on the SAR443820 treatment group incidence, alphabetic order in case of equal frequency.

Analysis of all adverse events in Part A and Part A + Part B

The overview of TEAE will be generated presenting the number (%) of participants with:

- Any TEAE
- Any severe TEAE
- Any treatment-emergent SAE
- TEAE leading to death
- Any TEAE leading to permanent intervention discontinuation of IMP
- Any treatment emergent AESI
- Any TEAE considered by the investigator as related to IMP

An additional overview summary including the number and rate of events will be provided.

The AE summaries of [Table 5](#) will be generated with number (%) of participants experiencing at least one event.

Listings of SAEs from randomized participants, AEs from participants who are treated but not randomized, AEs leading to treatment/study discontinuation and severe AEs will be provided.

Table 5 - Analyses of adverse events

Type of AE	MedDRA levels
All TEAEs	Primary SOC and PT
Common TEAE ($\geq 2\%$ in any group)	PT
TEAEs related to IMP as per Investigator's judgment	Primary SOC and PT
TEAE by maximal intensity	PT
Treatment emergent SAEs	Primary SOC and PT
Treatment emergent SAEs related to IMP as per Investigator's judgment	Primary SOC and PT
Treatment emergent AESIs	AESI category and PT
TEAEs leading to permanent intervention discontinuation	Primary SOC and PT
TEAEs leading to death ^b	Primary SOC and PT
Pretreatment AEs	Overview ^a
Post-treatment AEs	Primary SOC and PT

Type of AE	MedDRA levels

a Will include the following AE categories: any AEs, any serious AEs, any AEs leading to death
 
b Death as an outcome of the AE as reported by the Investigator in the AE page
	

Analysis of deaths in Part A and Part A + Part B

In addition to the analyses of deaths included in [Table 5](#), the number (%) of participants in the following categories will be provided:

- Deaths during the treatment-emergent period and post-treatment period
- Deaths in non-randomized participants or randomized but not treated participants

Analysis of adverse events of special interest (AESIs) in Part A and Part A + Part B

Adverse events of special interest (AESIs) will be selected for analyses as indicated in [Table 6](#). Number (%) of participants experiencing at least one event will be provided for each event of interest. Tables will be sorted as indicated in [Table 4](#). A listing of AESIs will also be provided.

Table 6 - Selections for AESIs

AESIs	Selection
Pregnancy of a female participant or female partner of a male participant	Dedicated CRF page (AECAT="PREGNANCY DATA")
Symptomatic overdose (serious or non-serious) with IMP	Dedicated CRF page (AECAT="OVERDOSE DATA"; must be symptomatic and AESI marked "Y")
Convulsions, seizures	CMQsn00079 for selection and AESI marked "Y"
Serious infections meeting SAE definitions criteria	SOC of Infections and Infestations, both AESER and AESI marked "Y"
Increase in ALT > 3 x ULN	Dedicated CRF page (AECAT="ALT INCREASE DATA") and AESI marked "Y"

